## 15.2 CoP: Stochastic Interventional Effects on Risk and Vaccine Efficacy

Another approach to studying correlates of protection involves estimating the effect of shifting the immune response marker distribution in the vaccinated individuals (Hejazi et al., 2020a). Specifically, we can consider the effect on

risk of a given endpoint of a controlled intervention that shifts the distribution of an immune response by  $\delta$  units, where  $\delta$  is an analyst-specified real number. Considering a counterfactual scenario in which we are able to intervene so as to modify the immune response induced by the vaccine (e.g., a hypothetical change in dose or other re-formulation of the vaccine), we take this hypothetical intervention to lead to an improved (if  $\delta > 0$ ) or lessened immune response (if  $\delta < 0$ ) relative to the current vaccine (at  $\delta = 0$ ). Using this framework, we can query the counterfactual risk of the endpoint under this hypothetical vaccine. Using notation established above, this quantity can be expressed as the mean of the counterfactual variable  $Y(1, S(1) + \delta)$ .

This approach is similar to the controlled effects approach described in Section 15.3, but with an important distinction. In the controlled effects approach, one assumes that it is possible to set S = s for all individuals in the population. For high values of s, this assumption may be unrealistic if the vaccine fails to be strongly immunogenic for some subpopulations. On the other hand, with the interventional approach, it is only required that individuals' immune responses be shifted relative to their observed immune response, which may be more plausible for some vaccines.

Under assumptions (Hejazi et al., 2020a), the main two of which being no unmeasured confounding and positivity (forms of both are also required for the Controlled VE CoP analyses), the counterfactual risk of interest  $E[Y(1, S(1) + \delta)]$  is identified by

$$E[P(Y = 1 \mid A = 1, S = S + \delta, X = x) \mid A = 1, X].$$

Examining this quantity across a range of  $\delta$  provides insight into the relative contribution of a given immune response marker in preventing the endpoint of interest.

Hejazi et al. (2020a) proposed nonparametric estimators that rely on estimates of the outcome regression (as described above) and the conditional density of the immune response marker in vaccinated participants. Their estimators efficiently account for two-phase sampling of immune responses and are implemented in the txshift package (Hejazi and Benkeser, 2020) for the R language and environment for statistical computing (R Core Team, 2020), available via both GitHub at https://github.com/nhejazi/txshift and the Comprehensive R Archive Network at https://CRAN.R-project.org/package=txshift.

These estimators will be applied to each of the five Day 57 antibody markers (without baseline adjustment) controlling for the same set of baseline risk factors that are controlled for in other analyses previously discussed. As with the mediation analysis approach described in Section 15.3, the procedure will leverage low-dimensional risk factors alongside parametric regression strategies and flexible conditional density estimators for endpoints with fewer than 100 observed cases (pooling over the randomization arms); however, more flexible learning techniques will be employed for modeling the outcome process for endpoints with a greater number of observed cases.

In particular, conditional density estimates of immune response markers will be principally based on a nonparametric estimation strategy that reconstructs the conditional density through estimates of the conditional hazard of the discretized immune response marker values (Hejazi et al., 2020a,d,c); this approach is an extension of the proposal of Díaz and van der Laan (2011). A Super Learner ensemble (van der Laan et al., 2007) of variants of this nonparametric conditional density estimator and semiparametric conditional density estimators based on Gaussinization of residuals will be constructed using the s13 R package (Coyle et al., 2020). In settings with limited numbers of case endpoints, the outcome process will be modeled as a Super Learner ensemble of a library of parametric regression techniques (as recommend by Gruber and van der Laan, 2010), while the library will be augmented with flexible regression techniques — including, for example, lasso and ridge regression (Tibshirani, 1996; Tikhonov and Arsenin, 1977; Hoerl and Kennard, 1970), elastic net regression (Zou and Hastie, 2003; Friedman et al., 2009), random forests (Breiman, 2001; Wright et al., 2017), extreme gradient boosting machines (Chen and Guestrin, 2016), light and efficient gradient boosting machines (Ke et al., 2017), multivariate adaptive polynomial and regression splines (Friedman et al., 1991; Stone et al., 1994; Kooperberg et al., 1997), and the highly adaptive lasso (van der Laan, 2017; Benkeser and van der Laan, 2016; Hejazi et al., 2020b) — as the number of endpoint cases grows.

These algorithm libraries will be coordinated to match those used in other CoP analyses.

Additionally, we recall that P(Y(0) = 1) = P(Y = 1 | A = 0) (in view of vaccine versus placebo randomization, as stated previously in Section 15.1) and may be estimated in the same way as for the analysis of controlled vaccine efficacy, thus yielding an estimate of stochastic interventional VE defined by

$$SVE(\delta) = 1 - \frac{E[P(Y=1 \mid A=1, S=S+\delta, X=x) \mid A=1, X]}{P(Y(0)=1)}.$$

Output of the analyses will be presented as point and 95% point-wise confidence interval estimates of  $E[Y(1, S(1)+\delta)]$  and of SVE(s) over the values of s for each of the Day 57 antibody markers, for each of a range of  $\delta$  spanning -2 to 2 on the standard unit scale for each antibody marker.

Lastly, just as for the controlled VE CoP analyses, these analyses will only be performed if diagnostics support plausibility of the positivity assumption. Importantly, however, the positivity assumption for the stochastic interventional effects differs from that usually required. That is, where the positivity assumption for effects defined by static interventions requires a positive probability of treatment assignment across all strata defined by baseline factors (i.e., that a discretized immune response value be possible regardless of baseline factors), the positivity assumption of these effects is

$$s_i \in \mathcal{S} \implies s_i + \delta \in \mathcal{S} \mid A = 1, X = x$$

for all  $x \in \mathcal{X}$  and i = 1, ..., n. In particular, this positivity assumption does not require that the post-intervention exposure density,  $q_{0,S}(S-\delta \mid A = 1, X)$ , place mass across all strata defined by X. Instead, it requires that the postintervention exposure mechanism be bounded, i.e.,

$$P\{q_{0,S}(S-\delta \mid A=1,X)/q_{0,S}(S \mid A=1,X) > 0\} = 1,$$

which may be readily satisfied by a suitable choice of  $\delta$ .

More importantly, the static intervention approach may require consideration of counterfactual variables that are scientifically unrealistic. Namely, it may be inconceivable to imagine a world where every participant exhibits high immune responses, given the phenotypic variability of participants' immune systems. This too may be resolved by considering an intervention  $\delta(X)$ , allowing the choice of  $\delta$  to be a function of baseline covariates X (Hejazi et al., 2020a; Díaz and van der Laan, 2012; Haneuse and Rotnitzky, 2013; Díaz and van der Laan, 2018).

## 15.3 CoP: Mediation of Vaccine Efficacy

Using mediation methods, we can decompose the overall VE into so-called *natural* direct and indirect effects. We will estimate this decomposition for each Day 57 antibody marker individually (focusing on the non-baseline sub-tracted markers as for the other CoP analyses described above), as well as when considering all antibody markers together (although this SAP currently restricts to analysis of the individual markers).

For simplicity, as before, we describe this approach using a binary outcome, noting that extensions to time-to-event (with competing risks) are possible. The *total* effect of the vaccine can be represented by one minus the risk ratio

$$RR = \frac{P(Y(1, S(1)) = 1)}{P(Y(0, S(0)) = 1)} .$$

The natural direct and indirect effects are, respectively,

$$\operatorname{RR}_{DE} = \frac{P(Y(1, S(0)) = 1)}{P(Y(0, S(0)) = 1)} \text{ and } \operatorname{RR}_{IDE} = \frac{P(Y(1, S(1)) = 1)}{P(Y(1, S(0)) = 1)}.$$

Note that  $RR = RR_{DE}RR_{IDE}$ , showing that the total effect decomposes into the direct times indirect effect. Another quantity of interest is the proportion mediated, which could be expressed as

$$PM = 1 - \frac{\log(RR_{DE})}{\log(RR)}$$

We note that PM=1 if and only if  $RR_{DE} = 1$ , i.e., no direct effect means that the marker fully mediates VE. We will estimate PM defined in this way.

As above, we must assume all confounders X of S and Y have been measured. We also assume there are no confounders of the mediator-outcome

relationship that are affected by treatment. Moreover, we require an overlap assumption that

$$P(S = s | A = 0, X = x) > 0$$
 implies  $P(S = s | A = 1, X = x) > 0$  (23)

for all subgroups X = x (i.e., a.e.). Under these assumptions, P(Y(a, S(a') = 1) is identified by

$$E[P(Y = 1 | A = a, S, X) | A = a', X]$$
.

In our immune CoP application it is expected that, for analyses restricting to baseline negative individuals, the conditional density of the immune response marker in the placebo arm will be a point mass at 0, that is with S below the LLOD. In other words, we do not expect any placebo recipients to have a positive value of the immune response marker. This implies the identification result that for a = 0, 1, P(Y(a, S(0)) = 1) = E[P(Y = 1 | A = a, S = 0, X)]. While P(Y(0, S(1) = 1) is not identified, it is not necessary to estimate this term in order for estimation of the parameters of interest (natural direct effect, natural indirect effect, PM).

For a highly immunogenic vaccine, it may be the case that the needed overlap assumption (23) will be violated. This could happen, for example if each baseline negative placebo recipient has antibody marker value below the assay's LLOD (which is expected), and every vaccine recipient has antibody marker value above the LLOD. We will only include antibody markers for mediation analysis if at least 10% of vaccine recipients have marker value equal to the value in placebo recipients.

Benkeser et al. (2021) provide a multiply robust targeted minimum loss-based plug-in estimator of natural direct and indirect effects that is appropriate for case-cohort sampling. The estimator requires estimation of several regressions, which are used in an augmented inverse probability of treatment weighted estimator. The propensity score will be estimated by a main terms logistic regression model to account for chance imbalances across randomization arms. The sequential outcome regressions used by the approach will be based on a super learner with the 14 algorithms listed in Table 9.

	Screens  /
Algorithms	Tuning Parameters
SL.mean	All
$\mathrm{SL.glm}$	Low-collinearity and (All, Lasso, LR)
SL.glm.interaction	(All, Lasso, LR)
SL.gam	Low-collinearity and (Lasso, LR)
SL.glmnet	All
SL.xgboost	All
SL.ranger	All

Table 9: Learning Algorithms in the super learner Library for mediation methods.

All = include all variables; Lasso = include variables with non-zero coefficients in the standard implementation of SL.glmnet that optimizes the lasso tuning parameter via 10-fold cross-validation; Low-collinearity = do not allow any pairs of quantitative variables with Spearman rank correlation > 0.90; LR = Univariate logistic regression Wald test 2-sided p-value < 0.10.

The estimator is implemented in the natmed2 package available on GitHub (https://github.com/benkeser/natmed2). The baseline covariates X adjusted for are the same as for the other analyses (e.g. of CoR and of Controlled vaccine efficacy).

# 16 Summary of the Set of CoR and CoP Analyses and Their Requirements and Contingencies, and Synthesis of the Results, Including Reconciling Any Possible Contradictions in Results

Table 10 summarizes all of the Stage 1 / Day 57 marker correlates analyses that are done, including contingencies for whether and when each analysis is done. The quantitative version of each marker S, and the tertiles version of each marker S, is common across all of the analyses. All of the Day 57 markers are the versions that are not baseline subtracted, given that the cohort for analysis is baseline negative. Most of the analyses focus on univariate Day 57 markers. The primary reason to do this is the goal to identify a parsimonious correlate based on a single marker without needing to run the

set of assays, and secondary reasons are: (1) the assay readouts are expected to be highly correlated, especially for the ID50 and cID80 readouts from the same pseudovirus neutralization assay, and (2) there is ample precedent for univariate markers being accepted as immunological surrogate endpoints for approved vaccines (Plotkin, 2010).

	Structure	Requirements/Contingencies	
	of	Min No. Vaccine	
Analysis	Day 57 Marker(s)	Endpoints	$\mathbf{Other}$
CoR Cox Model	Tertiles of $S^1$	25	None
	Quant. $S = s^2$	25	None
	Quant. $S \ge s^1$	25	None
CoR Nonpar. threshold	Quant. $S \ge s^1$	35	None
CoR GAM	Quant. $S = s^2$	35	None
CoR threshold log. regr.	Quant. $S = s^2$	25	None
CoR Superlearner 	Quant. $S = s$ , 2FR, 4FR	35	None
CoP: Correlates of VE	Binary $S$	50	None
	Quant. $S = s$	50	BIP with $R^2 \ge 0.25$
CoP: Controlled VE	Quant. $S = s$	50	Feasibility of positivity 
	Tertiles of $S = s$	50	Feasibility of positivity 
CoP: Stoch. Interv. VE	Quant. $S = s$	50	Feasibility of positivity 
CoP: Mediators of VE	Quant. $S = s$	50	Feasibility of positivity 
	Tertiles of $S$	50	Feasibility of positivity 

These analyses are harmonized in addressing the same scientific question of how does endpoint risk vary over vaccinated subgroups defined by S above a threshold.

These exploratory supportive analyses are harmonized in addressing the same scientific question of how does endpoint risk vary over vaccinated subgroups defined by S equal to a given marker value.

Only this Superlearner analysis uses data from multiple assays and multiple readouts as input features; the other analyses consider one Day 57 biomarker at a time. The positivity

assumptions are as follows. Controlled VE: P(S = s | A = 1, X) > 0 almost surely. Stochastic Interventional VE:  $s_i \in S \implies s_i + \delta \in S | A = 1, X = x$  for all  $x \in \mathcal{X}$  and i = 1, ..., n. Mediators of VE: P(S = s | A = 1, X) > 0 almost surely and

P(S = s | A = 0, X = x) > implies P(S = s | A = 1, X = x) > 0. The quantitative analysis will require that the largest value S observed in the placebo is larger than the smallest value of S observed in the vaccine recipients. This assumption would naturally be satisified for the tertiles analysis. For quantitative S, the assumption is weaker for the Stochastic Interventional VE analysis, such that it is possible that only this analysis of the three will be done.
Some of the analyses include parametric assumptions for characterizing associations (Cox model and threshold analyses, Cox model versions of Controlled VE analyses) and others are nonparametric or approximately so (all other analyses). If parametric and nonparametric analyses of the same type (e.g., Cox model vs. nonparametric CoR analysis of the same association parameter; Controlled VE Cox model vs. nonparametric monotone dose-response) suggest contradictory results, then the interpretation from the nonparametric analysis will be prioritized, given it is more robust and less likely to be an incorrect result. The diagnostic testing of the parametric assumptions will aid this interpretation. As noted above, if the nonparametric analysis suggesting a contradictory result requires a positivity assumption, then its results will only be prioritized if diagnostics support feasibility of the positivity assumption.

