The bAb assay readouts are in units AU/ml, where AU stands for arbitrary units from a standard curve. The process of validating the assay defined a lower limit of detection (LLOD), an upper limit of detection (ULOD), a lower limit of quantitation (LLOQ), an upper limit of quantitation (ULOQ), and a positivity cut-off for each antigen that defines positive vs. negative response. These values are as follows:

- bAb Spike:
  - Pos. Cutoff = 1204.71 AU/ml
  - LLOD = 34.18 AU/ml
  - ULOD = 19,136,250 AU/ml
  - LLOQ = 199.64 AU/ml
  - ULOQ = 1,128,438.87 AU/ml
- bAb RBD:
  - Pos. Cutoff = 517.86 AU/ml

- LLOD = 58.59 AU/ml
- ULOD = 8,201,250 AU/ml
- LLOQ = 125.9678 AU/ml
- ULOQ = 598,133.3615 AU/ml

• N:

- Pos. cutoff = 9779.62 AU/ml
- LLOD = 39.06 AU/ml
- ULOD = 21,870,000
- LLOQ = 1870.70 AU/ml
- ULOQ = 239,449.31

The Vaccine Research Center established factors for converting the MSD assay readouts from AU/ml to WHO International Units/ml, which is the same thing as Binding Antibody Units/ml (BAU/ml). For the three binding antibody variables CoV-2 Spike IgG, CoV-2 RBD IgG, and CoV-2 N IgG, these conversion factors are 0.0090, 0.0272, and 0.0024, respectively. These conversion factors are applied, such that all binding Ab readouts are reported in WHO International Units/ml with notation BAU/ml, following the WHO recommendation, for all analyses. These conversion factors are also applied to yield the LLOD, ULOD, LLOQ, and ULOQ on the WHO BAU/ml scale. The following shows the assay limits on the BAU/ml scale:

- bAb Spike:
  - Pos. Cutoff = 10.8424 BAU/ml
  - LLOD = 0.3076 BAU/ml
  - ULOD = 172,226.2 BAU/ml
  - LLOQ = 1.7968 BAU/ml
  - ULOQ = 10,155.95 BAU/ml
- bAb RBD:

- Pos. Cutoff = 14.0858 BAU/ml
- LLOD = 1.593648 BAU/ml
- ULOD = 223,074 BAU/ml
- LLOQ = 3.4263 BAU/ml
- ULOQ = 16,269.23 BAU/ml
- bAb N:
  - Pos. Cutoff = 23.4711 BAU/ml
  - LLOD = 0.093744 BAU/ml
  - ULOD = 52,488 BAU/ml
  - LLOQ = 4.4897 BAU/ml
  - ULOQ = 574.6783 BAU/ml

All values below the LLOD are assigned the value LLOD/2. For immunogenicity reporting, values greater than the ULOQ are not given a ceiling value of the ULOQ, the actual readouts are used. For the immune correlates analyses, values greater than the ULOQ are assigned the value of the ULOQ.

(2) **Pseudovirus-nAb assay**: A firefly luciferase (ffLuc) reporter neutralization assay for measuring neutralizing antibodies against SARS-CoV-2 Spikepseudotyped viruses

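### Mediation has two conflicting overlap gates, and the tertile version treated as automatically feasible can substantially understate the proportion mediated

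*Combined protocol and SAP*

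**What the plan says.** **Estimand.** SAP Section 15.3 defines PM = 1 − log(RR_DE)/log(RR), with the direct effect evaluated at S(0), the marker value under placebo. It notes that "no direct effect means that the marker fully mediates VE". For baseline-negative participants it expects that the "conditional density of the immune response marker in the placebo arm will be a point mass at 0", meaning below the LLOD. Section 15.1 also places the natural direct effect at the LLOD.

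**Coding.** Section 2.1 says of the binding assay: "All values below the LLOD are assigned the value LLOD/2". The neutralization assays follow the same convention.

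**Overlap rule in Section 15.3.** The analysis will "only include antibody markers for mediation analysis if at least 10% of vaccine recipients have marker value equal to the value in placebo recipients". The section's example of violated overlap is every placebo recipient below the LLOD and every vaccine recipient above it.

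**Overlap rule in Section 16, Table 10 footnote 4.** Quantitative mediation requires that the "largest value S observed in the placebo is larger than the smallest value of S observed in the vaccine recipients". The next sentence covers tertiles: "This assumption would naturally be satisified for the tertiles analysis".

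Table 10 lists both quantitative and tertile mediation, each from 50 vaccine endpoints. The SAP does not say which gate governs or how placebo recipients are assigned to a tertile.

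**The concern.** Whether a marker receives a mediation estimate depends on which section the analyst follows. The tertile exemption is the more serious part. Coarsening a marker does not produce vaccinees without antibody. If placebo recipients are put in the low category with vaccinees who have detectable titres, the risk of those vaccinees stands in for P(Y(1, S(0)) = 1). When they are better protected than a vaccinee with no antibody, part of the antibody effect is counted as direct effect and PM is too low. Section 16.1 gives agreement in magnitude and direction more weight than significance, so a falsely low PM would count against a true correlate of protection.

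**Working it through.** **1. The plan's own benchmark.** For a full mediator RR_DE = 1. At VE 90%, PM = 1 − log(1)/log(0.1) = 1. The same holds at any VE. The SAP gives no other PM figure.

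**2. The gates on constructed data.**

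| Situation | 10% rule | Footnote rule |
|---|---|---|
| All placebo at LLOD/2; about 15% of vaccine recipients at LLOD/2 | Pass | Fail (equal is not larger) |
| 1 of 120 placebo at 20 BAU/ml; all vaccine recipients above LLOD, minimum 1.9 BAU/ml | Fail (0%) | Pass |

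LLOD/2 is the lowest value the coding allows, so a placebo arm lying entirely there can never exceed the vaccine minimum. The 120 is 6 strata × 20 from Table 5. The chance of at least one detectable value among 120 is 1 − (1 − q)^120, which is 45%, 70% and 91% for assumed false-positive rates q of 0.5%, 1% and 2%. Such a value must also exceed the vaccine minimum for the rule to pass.

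**3. Tertile PM for a log-linear full mediator, 10% rule not applied.** Assumptions: vaccine log10 marker normal, no vaccine mass at the placebo value, placebo at LLOD/2. Let d = (vaccine mean − placebo value)/SD, and let b be the log-risk slope per SD.

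- b solves −b·d + b²/2 = log(1 − VE), so b = d − √(d² + 2·log(1 − VE)).
- Lowest-tertile risk relative to placebo: RR_DE = (1 − VE) × 3 × Φ(−0.431 + b).

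Worked case: cID50 with placebo at 2.42/2 = 1.21 IU (log10 0.083), assumed vaccine mean 2.4 and SD 0.5, VE 90%.

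- d = (2.4 − 0.083)/0.5 = 4.63; b = 0.527.
- RR_DE = 0.1 × 3 × Φ(0.096) = 0.161.
- PM = 1 − log(0.161)/log(0.1) = 0.21, against a true value of 1.

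Over assumed means 2.0 to 3.5, SD 0.45 to 0.7 and VE 70% to 94%, PM runs from 0.13 to 0.37. A simulation at d = 5 and VE 90% gave 0.194, matching the formula.

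**4. Threshold-type full mediator.** A share 1 − VE of vaccinees is unprotected and falls at the bottom of the marker range; the rest have no risk. Then RR_DE = min(1, 3(1 − VE)).

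| VE | RR_DE | PM |
|---|---|---|
| 95% | 0.15 | 0.37 |
| 90% | 0.30 | 0.48 |
| 80% | 0.60 | 0.68 |
| 66.7% or less | 1 | 1 |

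**5. The 10% rule applied to tertiles as well.** Let p0 be the share of vaccinees at the placebo value. Combinations where a full mediator cannot reach the stated VE are omitted.

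| Risk above the placebo level | p0 | VE | PM |
|---|---|---|---|
| Flat | 10% | 50–90% | 0.29–0.48 |
| Flat | 15% | 50–85% | 0.44–0.58 |
| Flat | 20% | 50–80% | 0.59–0.68 |
| Log-linear, SD 0.7 or 0.94 | 10% | 50–85% | 0.54–0.63 |
| Log-linear, SD 0.7 or 0.94 | 15–20% | 50–80% | 0.63–0.80 |

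Example, flat risk, p0 = 10%, VE 80%: risk in the remaining 90% is (0.20 − 0.10)/0.90 = 0.111; RR_DE = 3 × (0.10 + 0.233 × 0.111) = 0.378; PM = 1 − log(0.378)/log(0.2) = 0.40.

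**6. Lowest category set at the placebo level.** Its risk for a full mediator is the placebo risk, so RR_DE = 1 and PM returns to 1.

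**The case against.** The strongest reply is that Section 15.3 words its rule for the marker, not for one coding of it, and footnote 4 does not expressly lift it. On that reading the footnote adds a condition for the quantitative version and the 10% rule still screens tertiles. Every scenario in step 3 would then be excluded: about 0.003% of vaccinees fall below the LLOD in the worked case, and about 1% in the most overlapping corner (mean 2.0, SD 0.7). This stands as a limit on size. A reader might infer that the plan will report a full mediator as mediating only 10% to 30% of VE. The documents do not support that, because it needs the footnote to override Section 15.3, an assumed dose-response and assumed marker means. Step 5 shows, however, that the 10% rule reduces the bias without removing it.

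Placebo pooling is also not written down. It is inferred as the only reading that makes the tertile sentence true. Section 12.3.3 does set a lowest category at or below the LLOD when more than 20% of vaccinees are below it, and Section 16 calls the tertile version common to all analyses. If that coding carries over to mediation, the problem narrows to markers with 10% to 20% of vaccinees at the placebo value. The SAP does not state that it carries over.

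Nor is the footnote rule simply the weaker one: under the expected placebo distribution it is stricter. Participants with evidence of infection before 7 days after the Day 57 visit are excluded (Section 12.3.1), so a stray placebo value would have to come from an undetected infection or an assay false positive.

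Table 10 attaches a positivity requirement to the tertile row, Section 4.3 cancels analyses whose assumptions look infeasible, and Section 16.2 treats its flag as a guideline. These help, but the footnote that defines the requirement declares it met for tertiles.

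**Conclusion.** The concern holds in a limited form. The two gates are unreconciled and can give opposite answers; that follows from the text and the LLOD/2 coding alone. The tertile exemption moves the direct effect away from the placebo level whenever the lowest category includes vaccinees above it. PM for a full mediator is then understated if those vaccinees have lower risk than at the placebo level: about 0.13 to 0.37 under the log-linear, well-separated assumptions without the 10% rule, and about 0.3 to 0.8 in the scenarios run with it. There is no bias for a threshold-type mediator at VE of about 67% or below, or when the lowest category is the placebo level. The sizes rest on assumed dose-response shapes and marker distributions. The effect on the overall synthesis was not quantified.

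**What to change.** - Make the Section 15.3 rule (at least 10% of vaccine recipients at the placebo value) the single overlap gate for quantitative and tertile mediation, and cite it in Table 10.
- Delete the two footnote 4 sentences giving the maximum/minimum rule and the tertile exemption.
- For categorical mediation, define the lowest category as the placebo level (at or below the LLOD). Otherwise drop the tertile row under mediators of VE.
- Report PM as not estimable for any marker that fails the gate.

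Dropping tertile mediation outright is unnecessary if the lowest category is set this way. The cost is a change of SAP wording, and fewer markers will receive a PM estimate.
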